### 5.7.1.5. Immunogenicity

#### 5.7.1.5.1. Humoral assays

For ELISAs (H5-ELISA and mini-HA ELISA) and VNA the following results will be calculated: N, geometric mean§ and corresponding 95% CI of the actual values, and fold increases from baseline will be tabulated and graphically presented. *§calculate the mean and corresponding 95% CI of log10 transformed values, back-transform this mean [i.e., 10mean] and CI [i.e., 10CI].*

A sample is considered positive if the value is above the assay LLOQ.

A response will be defined as:

- if sample interpretation is negative at baseline and there is >4-fold increase from LLOQ (on the original scale), or,
- if sample interpretation is positive at baseline and there is a >4-fold increase from baseline (on the original scale).

Tables will show the sample positivity, responders, and the percentage of participants with a >2-fold increase.

Geometric mean ratios (GMR) § between active groups and placebo group (pooled across cohort 1 and 2), with corresponding 95% CIs will be estimated via an analysis of variance (ANOVA), using log-transformed post-baseline value as dependent variable and study group as independent variable. As a sensitivity analysis, the ANOVA may also be performed adjusting for the respective baseline titers, by including log-transformed baseline titer as additional covariate. *§by back-transform LSmean and corresponding 95% CI from ANOVA [i.e., 10LSmean] and CI [i.e., 10CI].*

Actual values and fold changes from baseline are tabulated and shown as dot plots with dots for participant values, and the corresponding geometric mean and 95% CI per time point for each assay.

In the graphs, original values will be displayed on the log10 scale. The actual values will be shown, even if they are below the LLOQ. The LLOQ cut-off will be visualized in the graph per assay. Participant profiles of the actual values over time will also be graphically presented. A correlation plot of H5 ELISA versus mini-HA ELISA will be provided for the most important time points (at minimum, Baseline, Day 29, and fold increase from Baseline at Day 29).

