Geometric mean ratios (GMR)§ between active groups and placebo group (pooled across cohort 1 and 2), with corresponding 95% CIs will be estimated via an analysis of variance (ANOVA), using log-transformed post-baseline value as a dependent variable and study group as independent variable. As a sensitivity analysis, the ANOVA may also be performed adjusting for the respective baseline value, by including log-transformed baseline value as an additional covariate. §by back-transform LSmean and corresponding 95%CI from ANOVA [i.e.,  $10^{\text{LSmean}}$ ] and CI [i.e.,  $10^{\text{CI}}$ ].

Fold changes from baseline will be shown as dot plots with dots for participant values, and the corresponding geometric mean and 95% CI per time point for each assay.

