For the Breadth coverage AUC, the following results will be calculated: N, mean and corresponding 95% CI, interquartile range, min, max of the actual values, and mean increases from baseline will be tabulated and graphically presented. Reverse cumulative breadth coverage plots for each group will be presented based on individual breadth coverage. Least square means between active groups and the placebo group (pooled across cohort 1 and 2), with corresponding 95% CIs will be estimated via an analysis of variance (ANOVA), using post-baseline value as a dependent variable and study group as independent variable. As a sensitivity analysis, the ANOVA may also be performed adjusting for the respective baseline value, by including baseline value as an additional covariate.

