### 5.7.1.6.2. Humoral assays

Descriptive statistics and graphs on humoral immunogenicity data listed in [Table 4](#) (where available) will be done similarly as described in section [5.7.1.5.1.](#) for the COV3005 Broad SF-SC cohort (H5 ELISA, mini-HA ELISA, VNA, Human Fc $\gamma$ RIIIa reporter assay, breadth ELISAs including three breadth scores, coverage score, and HAI assay) and for the SF-SC cohort.

For H5 ELISA, mini-HA ELISA, VNA, Human Fc $\gamma$ RIIIa reporter assay, and three breadth scores, geometric mean ratios (GMR)  $\ddagger$  between active groups (FLZ1001 vs. SF-SC cohort), with corresponding 95% CIs will be estimated via an analysis of variance (ANOVA), using log-transformed 28 days post-dose 1 immune parameter response as dependent variable and study group as independent variable. As a sensitivity analysis, the ANOVA may also be performed adjusting for the respective baseline titers, by including log-transformed baseline titer as an additional covariate.  $\ddagger$ by back-transform LSmean and corresponding 95%CI from ANOVA [i.e.,  $10^{LSmean}$ ] and CI [i.e.,  $10^{CI}$ ].

In addition, GMR plots over time, combining the regimens in one graph (without individual participant dots) will also be created.

For the breadth coverage, least square mean differences between active groups (FLZ1001 vs. SF-SC cohort), with corresponding 95% CIs will be estimated via an analysis of variance (ANOVA), using 28 days post-dose 1 breadth coverage as dependent variable and study group as independent variable. As a sensitivity analysis, the ANOVA may also be performed adjusting for the respective baseline value, by including baseline breadth coverage as an additional covariate.

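### The SAP's footnote formula for the geometric mean ratio back-transforms a group's LS mean, not the LS mean difference, so it contradicts the ratio it is meant to define

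*SAP*

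**What the plan says.** For the ELISAs and the neutralization assay, SAP section 5.7.1.5.1 plans GMRs "between active groups and placebo group (pooled across cohort 1 and 2), with corresponding 95% CIs will be estimated via an analysis of variance (ANOVA"), with the model "using log-transformed post-baseline value as dependent variable and study group as independent variable". An optional sensitivity analysis adds the baseline titer as a covariate. The footnote to the GMR gives the computation as "by back-transform LSmean and corresponding 95% CI from ANOVA", spelled out as 10^LSmean for the estimate and 10^CI for the interval.

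The formula recurs under Breadth Score ("by back-transform LSmean and corresponding 95%CI from ANOVA") and in section 5.7.1.6.2, for the GMRs of FLZ1001 groups against the SF-SC cohort from COV3005. Other assays, such as the FcγRIIIa reporter assay and the extended breadth scores, inherit it because they are to be analysed in a similar way.

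Two passages on Breadth Coverage, which is analysed without a log transformation, describe the same kind of comparison differently:
- Against placebo (the text after Table 6): "Least square means between active groups and the placebo group (pooled across cohort 1 and 2), with corresponding 95% CIs will be estimated".
- Against SF-SC (section 5.7.1.6.2): "least square mean differences between active groups (FLZ1001 vs. SF-SC cohort), with corresponding 95% CIs will be estimated".

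**The concern.** The footnote is the only place where the SAP says how a GMR and its interval are computed, and the computation does not give the quantity named. It is essentially the back-transformation that the same section gives for a single group's geometric mean (10^mean, 10^CI). One recipe cannot serve both for a group mean and for a ratio of two group means.

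The ANOVA comparisons are the only model-based between-group immunogenicity estimates in the SAP, and they include the secondary ELISA endpoint. As nothing is formally tested, their intervals are what a reader would use to judge uncertainty. The sponsor's committee draws on the immunogenicity results, among other factors, when it chooses a regimen (protocol section 9.5, SAP section 5.8). A formula that programmers and quality control may be checked against should produce what its label says.

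**Working it through.** **Inputs**
- Active arm: 25 randomized, 22 evaluable after an assumed 12% exclusion (protocol section 9.2).
- Pooled placebo: 10 + 10 = 20 (protocol Table 1). With the same 12% loss, 20 × 0.88 = 17.6, about 18. Equal loss on placebo is my assumption, so both 18 and 20 are shown.
- SD on the log10 scale: 0.181 to 0.783 (protocol Table 5).
- Model: one ANOVA with six active groups and pooled placebo, common SD, no covariate. Residual df = 6×22 + 18 − 7 = 143, or 145 with 20 placebo; t = 1.977 for 143 df.

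**1. The protocol's own figure.** Table 5 gives 90.0% power for a two-fold ratio at SD 0.301. A two-sample t-test (noncentral t, 22 against 22, 42 df, two-sided 0.05) gives 90.0%. All 18 non-null cells reproduce to within 0.2 percentage points. A one-sample or paired version gives 99.4% and does not fit. The planning figures therefore carry the standard error of a difference between two groups, and the footnote does not affect them.

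**2. What the footnote computes.** In a one-way ANOVA on log10 values, a group's LS mean is its mean log10 value.
- Footnote: 10^LSmean(active), half-width t × SD × √(1/n_active).
- Ratio: 10^(LSmean(active) − LSmean(placebo)), half-width t × SD × √(1/n_active + 1/n_placebo).

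Placebo data do enter the footnote's interval through the pooled residual SD. What is absent is the 1/n_placebo term.

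**3. Size of the absent term**, as a share of the variance of the difference:
- 18 placebo: (1/18) / (1/22 + 1/18) = 0.0556 / 0.1010 = 55%.
- 20 placebo: (1/20) / (1/22 + 1/20) = 0.0500 / 0.0955 = 52%.

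**4. Width.** On the log scale the interval for the difference is wider than the LS mean interval by √(0.1010/0.04545) = 1.49 (18 placebo) or √(0.0955/0.04545) = 1.45 (20 placebo), whatever the SD. As multiplicative limits:

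| SD (log10) | LS mean CI | Difference CI, 18 placebo | Difference CI, 20 placebo |
|---|---|---|---|
| 0.301 | ×/÷ 1.34 | ×/÷ 1.55 | ×/÷ 1.53 |
| 0.421 | ×/÷ 1.50 | ×/÷ 1.84 | ×/÷ 1.81 |
| 0.783 | ×/÷ 2.14 | ×/÷ 3.10 | ×/÷ 3.01 |

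For SD 0.421 and 18 placebo: 1.977 × 0.421 × √(1/22) = 0.177, and 10^0.177 = 1.50; 1.977 × 0.421 × √(1/22 + 1/18) = 0.265, and 10^0.265 = 1.84.

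**5. Illustration** (assumed geometric means 3000 active and 1000 placebo, SD 0.421, 22 against 18). The footnote gives 3000 (1994 to 4514). The ratio is 3.00 (1.63 to 5.52).

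**6. A hypothetical mix-up.** Suppose the ratio were computed correctly but given the LS mean half-width. Its half-width would be 1/1.49 = 0.67 (18 placebo) or 1/1.45 = 0.69 (20 placebo) of the correct one, and coverage of the nominal 95% interval would be 81.3% or 82.5%. The SAP does not prescribe this.

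**The case against.** The best defence is that the governing sentence already names the right quantity: a ratio between active and placebo groups, with its CI. On this view the footnote only explains the change of scale and drops the word difference. Section 5.7.1.6.2 says "least square mean differences between active groups (FLZ1001 vs. SF-SC cohort), with corresponding 95% CIs" for the parallel Breadth Coverage comparison, which shows that contrasts are meant. A literal 10^LSmean would stand out at once, since a value such as 3000 under a ratio heading is plainly in titer units. Programming instructions are placed in the Data Presentation Specifications (SAP section 1), which are not among the documents, so whether the footnote would be coded literally cannot be known.

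Most of this stands. The intent is clear, and an experienced programmer would probably take the contrast. The Breadth Coverage sentence against placebo ("Least square means between active groups and the placebo group (pooled across cohort 1 and 2") has no formula and is only loosely worded. What does not fall away is that the stated formula, given in three places, is wrong for the quantity it defines.

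A reader might infer that the trial will report GMR intervals that are too narrow, with about 81% to 83% coverage. The documents do not support that. It would take a hybrid of a correct ratio and a single-group half-width, which no section specifies. Taken literally, the footnote gives a valid interval for a geometric mean, under the wrong label.

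**Conclusion.** The point holds as a low-severity correction. The GMR footnote in section 5.7.1.5.1, under Breadth Score and in section 5.7.1.6.2 conflicts with the sentences it annotates and with the differences wording used for Breadth Coverage against SF-SC. Followed literally, it yields a group geometric mean whose CI omits the comparator mean's sampling error. Against placebo that is 52% to 55% of the variance of the difference, given 22 active participants, 18 to 20 pooled placebo participants and a common SD in an unadjusted ANOVA.

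The consequence is limited. No hypothesis is tested, no success threshold rests on a GMR, and the sample-size figures reproduce independently of the footnote. Group geometric means, fold rises and responder rates are unaffected. It would also go too far to infer that regimen selection is compromised, since the committee weighs safety, immunogenicity and other factors.

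I give no figure for the SF-SC comparison. Section 5.7.1.6.1 states no size for that cohort, and the 76 participants under Extended Breadth Score are the number selected for that analysis.

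**What to change.** In section 5.7.1.5.1 (titers), under Breadth Score, and in section 5.7.1.6.2, replace the GMR footnote with: *GMR = 10^(difference in LS means, active minus comparator); 95% CI = 10^(confidence limits of that difference from the ANOVA)*. The same text serves the baseline-adjusted sensitivity analysis, with adjusted LS means.

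In the Breadth Coverage text after Table 6, write *Least square mean differences between*, to match section 5.7.1.6.2. Check that the Data Presentation Specifications request the contrast.

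The cost is SAP wording only. It needs no new data and does not change the intended analysis.

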**Table 5: full-length HA breadth panel**

HA	Year	Strain	Rationale	Q**	Narrow H1 score	Broad Group 1 score	Group 1 score excl. H1	Breadth Coverage
H5	2005	A/Vietnam/1203/2004 (UFV190837)	Core assay	F		Y	Y	Y
H5*	2023	A/Cambodia/NPH230032/2023 (UFV235130)	Pandemic recent avian strain	P		Y	Y	Y
mH1 ^	2009	A/California/07/2009 (UFV180702)	H1 subtype, vaccine backbone	F				
mH1*	1999	A/New Caledonia/20/1999 (UFV190137)	H1 subtype, remote, benchmark VRC	P	Y	Y		
H1	2019	A/Victoria/2570/2019 (UFV221619)	H1 subtype	F	Y	Y		Y
H1	2009	A/California/07/2009 (UFV181009)	H1 subtype, vaccine backbone	F	Y	Y		Y
H1	1999	A/New Caledonia/20/1999 (UFV181089)	H1 subtype, remote, benchmark VRC	P	Y	Y		Y
H1	1918	A/South Carolina/1/1918 (UFV181084)	H1 subtype, oldest, pandemic	P	Y	Y		Y
H2	2005	A/Env/MPU3156/2005 (UFV181154)	Pandemic	P		Y	Y	Y
H2*	2020	A/avian/Japan/KU-d3c/2020 (UFV235127)	Pandemic recent avian strain	P		Y	Y	Y
H11	2009	A/Env/MPK655/2009 (UFV190050)	H11 clade, representative	F		Y	Y	Y
H17	2010	A/bat/Guatemala/060/2010-(UFV190401)	Bat strain, stable molecule	P		Y	Y	Y
H9	1999	A/Hong Kong/1073/1999 (UFV181156)	H9 clade, benchmark PATH	F		Y	Y	Y
H9*	2021	A/Cambodia/21020301/2021 (UFV235131)	Pandemic recent avian strain	P		Y	Y	Y
H7 ^	2013	H7N9 A/Anhui/1/2013 (UFV180438)	G2, pandemic, low pressure	E				
B ^	2017	B/Iowa/06/2017(UFV235091)	B, dominant Victoria lineage	E				

\* Included in extended breadth score only (are available only for subset of participants).

\*\* Q = Qualification status: P = partially qualified, F = fully qualified, E = exploratory.

^ mH1 (A/California/07/2009), H7 (H7N9 A/Anhui/1/2013), and B (B/Iowa/06/2017) will be reported separately and are not included in any breadth score.

Y = included in corresponding breadth score or breadth coverage calculation.

Each IgG ELISA from the breadth panel data will be presented in a similar way to the core ELISA assays as described above.

## **Breadth Score**

Three types of breadth scores will be calculated based on breadth panel assays, listed in [Table 5](#) using Maximum Diversity Weighting method ([Z. He, Y. Fong, Stat Med. 2019](#)) (R package: “mdw”):

- Narrow H1 score (H1 strains as identified in [Table 5](#)):
  - o Although the vaccine backbone mini-HA ELISA does assess an H1 HA, this ELISA may also measure neo-epitope immune responses against design elements of the protein, which could potentially result in an inflated mini-HA ELISA response in FLZ1001. Therefore, the vaccine backbone mini-HA ELISA (A/California/07/2009) results will be excluded from the H1 Breadth Score.
- Broad Group 1 score (Group 1 strains as identified in [Table 5](#)):
  - o The vaccine backbone mini-HA ELISA (A/California/07/2009) results will be excluded from the Group 1 Breadth Score (same reason as for Narrow H1 score).
  - o The H7 and B ELISAs will also be excluded from the Group 1 Breadth Score as these are Group 2 and Flu B antigens, respectively, and do not represent Group 1 HAs.
- Group 1 score excluding H1 (Group 1 strains as identified in [Table 5](#)):
  - o All H1 (including the mini-HA ELISA) results will be excluded from the Group 1 score excluding H1.
  - o The H7 and B ELISAs will also be excluded from the Group 1 score excluding H1 as these are Group 2 and Flu B antigens, respectively, and do not represent Group 1 HAs.

The Breadth score will be calculated for each participant only when all ELISAs used in the calculation are non-missing. For each ELISA included in the breadth score calculation, values below LLOQ will be imputed to LLOQ/2, and values above the upper limit of quantification (ULOQ) will be imputed with the ULOQ. Calculation of the breadth score is done separately at each analysis.

The following results will be calculated: N, geometric mean§ and corresponding 95% CI, interquartile range, min, max of the actual values, and fold increases from baseline will be tabulated and graphically presented. §calculate the mean and corresponding 95%CI of  $\log_{10}$  transformed values, back-transform this mean [i.e.,  $10^{\text{mean}}$ ] and CI [i.e.,  $10^{\text{CI}}$ ].

Geometric mean ratios (GMR)§ between active groups and placebo group (pooled across cohort 1 and 2), with corresponding 95% CIs will be estimated via an analysis of variance (ANOVA), using log-transformed post-baseline value as a dependent variable and study group as independent variable. As a sensitivity analysis, the ANOVA may also be performed adjusting for the respective baseline value, by including log-transformed baseline value as an additional covariate. §by back-transform LSmean and corresponding 95%CI from ANOVA [i.e.,  $10^{\text{LSmean}}$ ] and CI [i.e.,  $10^{\text{CI}}$ ].

Fold changes from baseline will be shown as dot plots with dots for participant values, and the corresponding geometric mean and 95% CI per time point for each assay.

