### 5.7.1.2. Handling of Missing and/or Unquantifiable Immune Response Data

Missing immune response data will not be imputed.

Values below the lower limit of quantification (LLOQ) will be imputed based on the type of analysis:

- For the calculation of the geometric mean titer, values below LLOQ will be imputed to LLOQ/2.
- For the calculation of the geometric mean of the increase from baseline and calculation of the Breadth Coverage, values below LLOQ will be imputed to LLOQ.

Data above the upper limit of quantification (ULOQ) will be imputed with the ULOQ.

The LLOQ or limit of detection [LOD], as applicable, and ULOQ values per assay are available in the database.

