**Table 6: Phylogenetic distance matrix**

HA	Strain	H1_Cal	H1_Vic	H1_SC	H1_NC	H2_2005	H2_2020	H5_cam	H5_Vnm	H11	H17	H9_HK	H9_Camb
H1	A/California/07/2009 (UFV181009)	0	0.05	0.15	0.24	0.45	0.43	0.49	0.47	0.63	0.71	0.74	0.73
H1	A/Victoria/2570/2019 (UFV221619)	0.05	0	0.18	0.25	0.45	0.43	0.5	0.47	0.62	0.69	0.72	0.71
H1	A/South Carolina/1/1918 (UFV181084)	0.15	0.18	0	0.16	0.39	0.37	0.46	0.43	0.61	0.67	0.64	0.69
H1	A/New Caledonia/20/1999 (UFV181089)	0.24	0.25	0.16	0	0.45	0.42	0.47	0.47	0.64	0.7	0.68	0.7
H2	A/Env/MPU3156/2005 (UFV181154)	0.45	0.45	0.39	0.45	0	0.03	0.3	0.28	0.62	0.65	0.66	0.7
H2*	A/avian/Japan/KU-d3c/2020 (UFV235127)	0.43	0.43	0.37	0.42	0.03	0	0.29	0.27	0.59	0.63	0.65	0.68
H5*	A/Cambodia/NPH230032/2023 (UFV235130)	0.49	0.5	0.46	0.47	0.3	0.29	0	0.1	0.61	0.69	0.73	0.78
H5	A/Vietnam/1203/2004 (UFV190837)	0.47	0.47	0.43	0.47	0.28	0.27	0.1	0	0.59	0.68	0.7	0.77
H11	A/Env/MPK655/2009 (UFV190050)	0.63	0.62	0.61	0.64	0.62	0.59	0.61	0.59	0	0.79	0.69	0.69
H17	A/bat/Guatemala/060/2010-(UFV190401)	0.71	0.69	0.67	0.7	0.65	0.63	0.69	0.68	0.79	0	0.79	0.77
H9	A/Hong Kong/1073/1999 (UFV181156)	0.74	0.72	0.64	0.68	0.66	0.65	0.73	0.7	0.69	0.79	0	0.15
H9*	A/Cambodia/21020301/2021 (UFV235131)	0.73	0.71	0.69	0.7	0.7	0.68	0.78	0.77	0.69	0.77	0.15	0

The Breadth coverage area under the curve (AUC) will be calculated for each participant only when all ELISAs used in the calculation are non-missing. For each ELISA included in the breadth coverage calculation, values below LLOQ will be imputed with the LLOQ, and values above the upper limit of quantification (ULOQ) will be imputed with the ULOQ. All ELISA values will be normalized to  $\log_{10}$  [original value / LLOQ value] prior to calculation of the Breadth coverage.

Breadth coverage plots will be generated based on all relevant IgG binding ELISAs and their distance factors for each subject. To quantify the coverage of breadth of binding ELISAs, the area under the curve (AUC) will be calculated by using the trapezoidal rule. Breadth coverage plots and AUC calculations will be generated and performed using R package “tidyverse” and “ggprism”.

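### Fold increases of the breadth scores fall under two conflicting SAP rules for values below LLOQ: LLOQ/2 in the Breadth Score paragraph, LLOQ in Section 5.7.1.2

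*SAP*

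**What the plan says.** SAP Section 5.7.1.2 chooses the imputed value by type of analysis. For levels: "For the calculation of the geometric mean titer, values below LLOQ will be imputed to LLOQ/2". For rises, the rule covers the "geometric mean of the increase from baseline and calculation of the Breadth Coverage, values below LLOQ will be imputed to LLOQ".

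The Breadth Score paragraph in Section 5.7.1.5.1 defines three scores by Maximum Diversity Weighting and gives one rule for their components: "For each ELISA included in the breadth score calculation, values below LLOQ will be imputed to LLOQ/2". It then lists the outputs of the score, including "interquartile range, min, max of the actual values, and fold increases from baseline will be tabulated and graphically presented". It does not say that the score is recalculated for the fold increases, or that it overrides Section 5.7.1.2. The Extended Breadth Score paragraph says its analysis is done in a similar way.

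Three neighbouring rules matter:

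- Each breadth-panel ELISA is presented like the core ELISAs, so its own fold increase falls under Section 5.7.1.2 and uses LLOQ.
- The responder definition measures a baseline-negative participant's rise from LLOQ, not from LLOQ/2.
- For Breadth Coverage, built largely from the same ELISAs: "For each ELISA included in the breadth coverage calculation, values below LLOQ will be imputed with the LLOQ".

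**The concern.** The two rules give different values for the same reported output. A programmer who follows the Breadth Score paragraph literally forms fold increases from a score with LLOQ/2 in it. One who follows Section 5.7.1.2 uses LLOQ. The SAP does not settle which is right.

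The tables can also contradict each other. If every component of a score starts below LLOQ and ends at 4 times LLOQ, each component table shows a 4-fold rise while the composite shows an 8-fold rise. A weighted average that exceeds all its parts is an artefact of the mixed convention.

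The size of the effect depends on how much of the score crosses LLOQ, so it can differ between regimens and need not cancel when their fold rises are compared. Protocol Section 9.2 bases immunogenicity on ratios of each timepoint to baseline, fold-change plots of the score are planned, and SAP Section 5.8 says immunogenicity results feed the choice of regimen.

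**Working it through.** The plan states no figure on this point, so there is nothing to reproduce. The effect of the two rules can be derived directly.

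**Inputs.** The imputation rules are those quoted from the SAP. Component counts come from SAP Table 5: Narrow H1 has 4, Broad Group 1 has 9 and Group 1 excluding H1 has 5. The extended versions have 5, 13 and 8. LLOQ values and below-LLOQ shares are not in the documents.

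**Formula.** Take the score as a weighted mean of log10 values with fixed weights summing to 1. Replacing LLOQ by LLOQ/2 subtracts log10(2) = 0.301 times the weight of the components below LLOQ, at each timepoint. For one participant:

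(fold with LLOQ/2) ÷ (fold with LLOQ) = 2^(W_up − W_down)

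W_up is the weight of components moving from below to above LLOQ, and W_down the weight moving the other way. For a group geometric mean, the exponent is the average of W_up − W_down.

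**Single-assay check (LLOQ = 1).**

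- Baseline below LLOQ, later value 4: 4/0.5 = 8 under LLOQ/2; 4/1 = 4 under LLOQ.
- Baseline 2, later value below LLOQ: 0.5/2 = 0.25 under LLOQ/2; 1/2 = 0.5 under LLOQ.
- Both values below, or both above: no difference.

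**Group level.** Net crossing weights of 10%, 25%, 50% and 100% give 2^0.10 = 1.07, 2^0.25 = 1.19, 2^0.50 = 1.41 and 2^1 = 2.00.

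**One crossing component, equal weights.** 2^(1/4) = 1.19 for Narrow H1, 2^(1/5) = 1.15 for Group 1 excluding H1 and 2^(1/9) = 1.08 for Broad Group 1.

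**Simulation.** Assumptions, none from the documents: 9 equally weighted components correlated at 0.6 within a person; 25 participants; 2000 replicates; log10 between-person SD 0.4 and within-person SD 0.1 or 0.2; about 7% to 93% of baseline values below LLOQ; true rises of 1 (placebo), 2 (seasonal-vaccine cohort), and 4 or 10 (active).

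The ratio of the two geometric mean fold rises was 1.05 to 1.70 in active groups, 1.04 to 1.21 in the seasonal-vaccine cohort and 1.00 in placebo. Within placebo, 10% to 33% of participants had a larger fold under LLOQ/2 (by up to 1.71) and about as many had a smaller one, so the mean is unmoved but the spread widens.

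For a true 4-fold rise with within-person SD 0.1:

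| Baseline below LLOQ | Fold, LLOQ/2 | Fold, LLOQ |
|---|---|---|
| 7% | 4.07 | 3.88 |
| 25% | 4.10 | 3.49 |
| 50% | 3.80 | 2.82 |
| 75% | 3.00 | 2.07 |

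In every row LLOQ/2 is nearer to 4.

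**The case against.** The strongest reply is that a specific rule overrides a general one. Section 5.7.1.2 names Breadth Coverage under the LLOQ rule and does not name the Breadth Score, which has its own rule. That reading is possible, but the SAP does not state it, and the paragraph can equally be read as fixing the level of the score only.

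Other parts of the defence stand:

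- The LLOQ rule is not shown to be nearer the truth. In the simulation it understated a true 4-fold rise by more than LLOQ/2 missed it.
- The ratios of active groups to placebo, and of the trial's groups to the seasonal-vaccine (SF-SC) cohort, are estimated from post-baseline values. For these, LLOQ/2 agrees with the rule for titers. Only the fold tables and plots change with the choice, plus, to a lesser degree, the optional baseline-adjusted ANOVA.
- The contrast with Breadth Coverage proves little by itself. That measure works on log10(value/LLOQ), where LLOQ gives a floor of zero, and it reports mean increases rather than fold increases.
- Breadth is exploratory, no immunogenicity hypothesis is tested, and the secondary H5 and mini-HA ELISA outputs are untouched. The fold rise of each component ELISA is also reported, which gives readers a check.
- The weights are estimated from the data and the SAP does not state scaling before weighting. The formula therefore holds for fixed weights on the log scale.

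None of this reconciles the two paragraphs.

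**Conclusion.** The inconsistency is real and should be resolved. For fold increases of the Breadth Score and Extended Breadth Score, the SAP supports two values that differ by 2^(net weight crossing LLOQ). That is roughly 1.04 to 1.7 for responding groups under the assumed below-LLOQ shares, with an absolute ceiling of 2. The actual size is unknown until those shares are known.

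Three stronger readings are tempting, and the documents do not support them:

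- A reader might infer that only the active arms are affected. One rule covers every group: the SF-SC cohort shifts too if it responds, and individual placebo participants shift in both directions.
- A reader might infer that breadth rises will be about doubled. That needs every weighted component to cross LLOQ. Nothing in the documents shows that baseline antibody to the panel is that low, and Protocol Section 8.1 expects pre-existing immunity to be measurable.
- A reader might infer that LLOQ/2 overstates the true rise. It gives larger fold rises than the SAP's own LLOQ rule, which is a different statement.

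**What to change.** In the Breadth Score and Extended Breadth Score paragraphs, state that score levels and geometric mean ratios use LLOQ/2. State that fold increases from baseline are computed from the score with values below LLOQ set to LLOQ, as Section 5.7.1.2 already requires, using the same diversity weights as the level score. Naming the weights matters, because re-estimating them under the second imputation would change the composite for another reason. Show the LLOQ/2 fold increases as a sensitivity analysis, and name the breadth scores in Section 5.7.1.2 so the two places agree.

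The cost is a short text change, one extra derived variable and one extra set of fold outputs, with no new data. Reported breadth fold rises become more conservative, and where many baseline values are below LLOQ they may understate the true rise. The sensitivity analysis lets a reader see by how much the choice matters.
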